10.5 Evaluating Adverse Events

10.5.1 Assessment of Intensity

The investigator or medically qualified designee will make an assessment of intensity for each AE reported during the study and will assign it to one of the following categories:

- Mild: An event that is easily tolerated by the subject, causing minimal discomfort and not interfering with everyday activities.
- Moderate: An event that is sufficiently discomforting to interfere with normal everyday activities
- Severe: An event that prevents normal everyday activities.

NOTE: An AE that is assessed as severe should not be confused with an SAE. Severe is a category utilized for rating the intensity of an event; and both non-serious AEs and SAEs can be assessed as severe. For example, a headache may be severe (interferes significantly with the subject's usual function) but would not be classified as serious unless it met one of the criteria for SAEs, listed above. An event is defined as 'serious' when it meets at least 1 of the predefined outcomes as described in the definition of an SAE, NOT when it is rated as severe.

10.5.2 Assessment of Causality

The causality assessment is one of the criteria used when determining regulatory reporting requirements.

For each AE (serious and non-serious), the investigator (or medically qualified designee) **must** provide an assessment of causality on the AE CRF page and the SAE form (subject to the classification of the AE). The investigator will also document in the medical notes that they have reviewed the AE and assessed causality, where applicable.

A "reasonable possibility" of a relationship conveys that there are facts, evidence, and/or arguments to suggest a causal relationship, rather than a relationship cannot be ruled out. Generally, the facts (evidence) or arguments to suggest a causal relationship should be provided.

The investigator will use clinical judgment to determine the relationship and will also consult the Safety Statement, in the determination of their assessment. Alternative causes, such as underlying disease(s), concomitant therapy, other risk factors, and the temporal relationship of the event to the study product will be considered and investigated.

For each AE/SAE, the investigator must document in the medical notes that they have reviewed the AE/SAE and has provided an assessment of causality.

The investigator's assessment of causality must be provided for all AEs (serious and non-serious); the investigator must record the causal relationship in the CRF, as appropriate, and report such an assessment in accordance with the SAE reporting requirements if applicable.

There may be situations when an SAE has occurred, and the investigator has minimal information to include in the initial report to the sponsor. **However, it is very important that the investigator always make an assessment of causality for every event prior to the initial transmission of the SAE data to the sponsor.** The investigator may change their opinion of causality in light of follow-up information and send an SAE follow-up report with the updated causality assessment.

10.6 Follow-up of AEs and SAEs

After the initial AE/SAE report, the investigator is required to proactively follow up with each subject and provide further information on the subject's condition.

All AEs (serious and non-serious) will be followed until resolution, until the condition stabilizes, until the event is otherwise explained, or until the subject is lost to follow-up.

The investigator is obligated to perform or arrange for the conduct of supplemental measurements and/or evaluations as may be indicated or as requested by the sponsor to elucidate as fully as possible the nature and/or causality of the AE. This may include additional laboratory tests or investigations, histopathological examinations, or consultation with other health care professionals.

New or updated information will be recorded on the AE CRF page and on the SAE form (subject to the classification of the AE).

The investigator will submit any updated SAE data to the sponsor within 24 hours of receipt of the information.

Investigators are not obliged to actively seek AEs in former subjects. However, if the investigator learns of a SAE, including death, at any time after a subject has been discharged from the study, and considers the event reasonably related to the study product or study participation, the investigator will promptly notify the sponsor by emailing the information to the Case Management Group mailbox at PPD [REDACTED], with copy to the appropriate CH Study Manager.

The investigator will submit any updated SAE data to the sponsor within the designated reporting time frames.

10.7 Withdrawal Due to an Adverse Event

Withdrawal due to AEs should be distinguished from withdrawal due to other causes, according to the definition of an AE noted earlier, and recorded on the appropriate AE CRF page.

When a subject withdraws because of an SAE, the SAE must be reported in accordance with the reporting requirements defined.

10.8 Regulatory Reporting Requirements for SAEs

The sponsor has a legal responsibility to notify, as appropriate, the local regulatory authority and other regulatory authorities about the safety of a product under clinical investigation. Prompt notification of SAEs by the investigator to the sponsor is essential so that legal obligations and ethical responsibilities towards the safety of subjects are met.

The sponsor will comply with country specific regulatory requirements relating to safety reporting to the regulatory authority, IRB/EC and investigators.

Both the investigator and the sponsor will comply with all local medical device reporting requirements

Investigator safety reports must be prepared for suspected unexpected serious adverse reactions (SUSAR) according to local regulatory requirements and sponsor policy and forwarded to investigators as necessary.

An investigator who receives an investigator safety report describing a SAE or other specific safety information e.g. summary or listing of SAE from the sponsor will review and then file it along with the Investigator's Brochure in the investigator study master file, and will notify the IRB/IEC, if appropriate according to local requirements.

10.9 Pregnancy

10.9.1 Time Period for Collecting Pregnancy Information

Pregnancy information will be collected on all pregnancies reported while a female subject is participating in the study from the signing of informed consent until 5 days after last administration of study product.

10.9.2 Action to be Taken if Pregnancy Occurs

The investigator will record pregnancy information on the appropriate form scan and e-mail it to the Case Management Group mailbox PPD [REDACTED], with copy to the appropriate CH Study Manager. Original pregnancy information forms will be retained in the investigator study master file.

The subject will be followed to determine the outcome of the pregnancy. Information on the status of the mother and infant / neonate (including concomitant medications taken by the mother during the pregnancy) will be forwarded by the investigator to the Case Management Group mailbox at PPD [REDACTED] with copy to the appropriate CH Study Manager. Generally, follow-up will be no longer than 6 to 8 weeks following the estimated delivery date. Any termination of the pregnancy will be reported.

While pregnancy itself is not considered to be an AE, abnormal pregnancy outcomes (e.g. spontaneous abortion, fetal death, stillbirth, congenital anomalies, ectopic pregnancy) are, and should be recorded as an SAE.

Any female subject who becomes pregnant while participating will be withdrawn from the study.

10.10 Medical Device Incidents

Both the investigator and the sponsor will comply with all local medical device reporting requirements.

Medical devices are being provided by the sponsor for use in this study; the medical device in this study is the supplied toothbrush.

10.10.1 Definition of an Incident

A medical device incident is any malfunction or deterioration in the characteristics and/or performance of a device as well as any inadequacy in the labeling or the instructions for use which, directly or indirectly, might lead to or might have led to the death of a subject/user/other person or to a serious deterioration in their state of health.

Not all incidents lead to death or serious deterioration in health. The nonoccurrence of such a result might have been due to other fortunate circumstances or to the intervention of health care personnel.

It is sufficient that:

An **incident** associated with a device happened and

- The **incident** was such that, if it occurred again, might lead to death or a serious deterioration in health.
- A serious deterioration in state of health can include any of the following:
 - Life-threatening illness
 - Permanent impairment of body function or permanent damage to body structure
 - Condition necessitating medical or surgical intervention to prevent one of the above
 - Fetal distress, fetal death, or any congenital abnormality or birth defects

Examples of incidents:

- A subject, user, caregiver, or healthcare professional is injured as a result of a medical device failure or its misuse.

- A subject's study treatment is interrupted or compromised by a medical device failure.
- A misdiagnosis due to medical device failure leads to inappropriate treatment.
- A subject's health deteriorates due to medical device failure.

10.11 Reporting of Incidents and Malfunctions

All incidents must be reported to the sponsor **immediately and under no circumstance should this exceed 24 hours** of the investigator or designee becoming aware of the situation.

Any medical device incident occurring during the study will be documented in the subject's medical records, if in accordance with the investigator's normal clinical practice, and on the appropriate Incident Report Form. In addition, for incidents fulfilling the definition of an AE (serious and non-serious), the appropriate AE CRF page and SAE form will be completed and reported as per the AE and SAE reporting sections.

The Incident Report Form will be completed as thoroughly as possible and signed by the investigator before transmittal to the sponsor. It is very important that the investigator describes any corrective or remedial actions taken to prevent recurrence of the incident.

The completed Incident Report Form should be scanned and emailed to the Case Management Group mailbox **PPD** (), with copy to the appropriate CH Study Manager, with the study number and subject number in the subject line of the email **immediately and under no circumstance should this exceed 24 hours** after study site personnel learn of the event. If there is an SAE, the completed SAE form should be sent together with this report form. However, if a copy of the SAE report is sent with this form, this does not replace the procedure to report an SAE. The original Incident Report Form will be retained in the investigator study master file.

The initial report will be followed up with more information as relevant, or as requested by the CH study manager.

The investigator will follow the following directions regarding the reporting of a device failure (malfunction):

- Notify the sponsor immediately (by following the process described above).
- Schedule the subject to return to the site promptly to return the failed device.
- Record any incidents on the CRF and Incident Report Form following instructions given in the section above.
- For any incident/malfunction occurring with a medical device (including those that are part of combination products) supplied by the sponsor, return the failed device to the sponsor as soon as possible, including documentation of the details of the failure.
- For any incident/malfunction occurring with a medical device (including those that are part of combination products) supplied by the Investigator site, report the incident to the device manufacturer and follow the manufacturer instructions for the return of the failed device (whilst keeping the sponsor informed).

10.12 Follow-up of Medical Device Incidents

Medical device incidents involving an AE will be followed and reported in the same manner as other AEs. This applies to all subjects, including those who discontinue study product or are withdrawn from the study.

The investigator is responsible for ensuring that follow-up includes any supplemental investigations as indicated to elucidate the nature and/or causality of the incident.

New or updated information will be recorded on the originally completed Incident Report form with all changes signed and dated by the investigator.

10.13 Regulatory Reporting Requirements for Medical Device Incidents

To fulfill regulatory reporting obligations worldwide, the investigator is responsible for the detection and documentation of events meeting the definitions of incident or malfunction that occur during all periods of the study in which the medical device is used.

The investigator will promptly report all incidents occurring with any medical device provided for use in the study in order for the sponsor to fulfill the legal responsibility to notify appropriate regulatory authorities and other entities about certain safety information relating to medical devices being used in clinical studies.

The investigator, or responsible person according to local requirements (e.g. the head of the medical institution), will comply with the applicable local regulatory requirements relating to the reporting of incidents to the IRB/IEC.

11 DATA MANAGEMENT

As used in this protocol, the term CRF is understood to refer to either a paper form or an electronic data record or both, depending on the data collection method.

For this study, subject data will be entered into an electronic CRF (eCRF), using a validated system. Data relating to SAEs, pregnancy and incidents will also be collected on paper forms.

The investigator is responsible for verifying that data entries are accurate and correct by physically or electronically signing the CRF.

The source documents (e.g. hospital records, clinical and office charts, laboratory notes, memoranda, subject diaries, questionnaires, evaluation checklists, pharmacy dispensing records, recorded data from automated instruments, microfiches, photographic negatives, microfilm or magnetic media, x-rays, subject files and records kept at the pharmacy, at the laboratory and at the medico-technical departments involved in the clinical study) which contain the source of data recorded in the CRF should be specified. The CRF and or diary can be used as a source document at the discretion of data management.

Each subject will be assigned and identified by a unique Screening Subject Number. Any reference made to an individual subject within the study must be done using their unique Screening Subject Number.

11.1 Case Report Form

A CRF is a printed, optical, or electronic document designed to record the protocol required information to be reported to the sponsor on each trial subject.

For each subject who has given informed consent/assent the CRF must be completed and signed by the Principal Investigator (or authorized designee) to certify that the data are complete and correct. The investigator must maintain accurate documentation (source data) that supports the information entered in the CRF.

Management of clinical data will be performed in accordance with Third Party BDM Vendor applicable standards and data cleaning procedures with oversight by the sponsor to ensure integrity of the data, for example, to correct errors and inconsistencies in the data.

To protect the privacy of subjects, no Personal Information (PI) (including the subject's name or initials or full birth date) is to be recorded in the CRF or as part of the query text.

All CRF pages should be completed during a subject assessment when the CRF has been designated as the source. Data that is sourced elsewhere should be entered into the CRF in an agreed upon timeframe between the Investigator and sponsor.

The sponsor will obtain and retain all CRFs and associated study data as applicable at the completion of the study.

11.2 Data Handling

Documentation of all data management activities should allow step-by-step retrospective assessment of data quality and study performance.

Any changes or corrections to data will be performed in the Electronic Data Capture (EDC) System, and it will include rationale for changes. The EDC system has an audit trail, which will provide a complete record of the changes and corrections endorsed by the Investigator.

Adverse events will be coded using Medical Dictionary for Regulatory Activities (MedDRA) and any concomitant medications terms (if applicable) using a validated medication dictionary, WHODrug.

11.2.1 Data Queries

Programmed edit checks will be generated automatically, as the data are being entered into the system. Reports and listings on the CRF data will also be run, in addition to the queries already programmed and generated by the system, to raise manual queries as needed for site clarification or correction. The sponsor's third party vendor will raise queries as needed on safety data to code the terms (AEs and Drugs or concomitant medication) appropriately.

The study monitor will perform ongoing review of the CRFs in accordance with the monitoring plan, to confirm that data entered into the CRF by authorized site personnel are accurate, complete, and verifiable from source documents; that the safety and rights of participants are being protected; and that the study is being conducted in accordance with the currently approved protocol and any other study agreements, ICH GCP, and all applicable regulatory requirements.

Any queries will be generated in the EDC System to the Investigator or designee, enabling the errors to be addressed in parallel with Data Management review. The study monitor can also run reports and listings on the CRFs, to raise manual queries as needed for site clarification or correction.

12 STATISTICAL CONSIDERATIONS AND DATA ANALYSES

12.1 Sample Size Determination

The study will be powered sufficiently (>90%) to provide evidence of superiority for an Experimental Dentifrice compared to the Reference Dentifrice for both stain removal and whitening after 8 weeks under the graphical approach method (with initial two-sided alpha

allocation of 5% for testing within each Experimental Dentifrice) to adjust for multiple comparisons and preserve a two-sided 10% family wise error rate as described in section 12.3.

Table 12-1 Sample Size Power by Endpoint at 5% and 2.5% Significance Levels with 90 Subjects per Arm

Endpoint at Week 8	Assumptions		Independent power from 90 subjects per arm for each endpoint by two-sided significance level ³		Power from graphical approach to achieve statistical significance at 5% level ⁴
	Mean Difference	Standard Deviation (SD)	5%	2.5%	
Within Experimental Dentifrice change from baseline in mean Total MLSI (Area x Intensity) ¹	0.6	0.4	>99.9%	>99.9%	>99.9%
Comparison with Reference Dentifrice in change from baseline in mean Total MLSI (Area x Intensity) ¹	0.3	0.4	99.8%	99.7%	99.8%
Within change from baseline in the mean VITA shade score ²	2	2	>99.9%	>99.9%	>99.9%
Comparison with Reference Dentifrice in change from baseline in the mean VITA shade score ²	1	2	91.5%	86.1%	90.2%

1) Estimates of mean difference and SD were based on results from previous GSKCH studies of similar design

CCI [REDACTED]

2) Estimates of mean difference and SD were based on results from a previous GSKCH study of similar design

CCI [REDACTED] Within treatment study reductions in the mean VITA shade score are expected to be greater in this study due to greater baseline VITA shade scores and an 8 week primary assessment instead of 4 weeks. As such, the SD is also assumed to increase, so an effect size (mean difference/SD) of 0.5 is assumed.

3) Based on carrying out a two tailed one-sample (within Experimental Dentifrice) or two-sample (Comparison with Reference Dentifrice) t-test at the 5% significance level using PASS software version 19.0.1.

4) Simulation using SAS 9.4 software based on stated assumptions for all endpoints and graphical approach analysis detailed in section 12.3.

As detailed in the independent sample size calculations in Table 12-1, the minimum required sample size assessment depends almost entirely on the mean VITA shade score reduction comparison between Experimental and Reference Dentifrices. Simulation shows that under the graphical approach methodology (Section 12.3) and the above underlying assumptions for an Experimental Dentifrice, the power to show statistical significance in all 4 comparisons for that Experimental Dentifrice (reduction from baseline and superior reduction compared to Reference Dentifrice in both mean Total MLSI [Area x Intensity] and mean VITA shade score) is > 90%.

Approximately 100 subjects per group (approximately 300 in total) will be randomized to account for a drop-out rate of up to 10% prior to Week 8.

Property of GSK Consumer Healthcare - Confidential

May not be used, divulged, published or otherwise disclosed without the consent of GSKCH

CCI [REDACTED]

Clinical Protocol Template v9.0

Page 51 of 63

12.2 Populations for Analysis

12.2.1 Definitions of Analysis Populations

The Safety population will include all randomized subjects who complete at least one use of study product. This population will be based on the study product the subject received. All assessments of safety will be based on this analysis population.

The modified Intent-To-Treat (mITT) population will include all randomized subjects who complete at least one use of study product and have at least one post baseline efficacy assessment. This population will be based on the study product to which the subject was randomized. All assessments of efficacy will be primarily based on this analysis population.

The per protocol (PP) population is defined as all subjects in the mITT population who have at least one assessment of efficacy considered unaffected by protocol violations.

12.2.2 Exclusions of Data from Analysis

Exclusion of any data from the analyses will be determined during a Blinded Data Review (BDR) Meeting prior to database lock. Any reasons for exclusion from an analysis population will be listed, if applicable.

A PP analysis will be performed on the mean Total MLSI (Area x Intensity) and mean VITA shade score endpoints if there is more than 10% difference in the number of subjects between the PP and mITT populations. A decision on whether a PP analysis will be performed will be made prior to study unblinding (release of the randomization codes).

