3.4 Timepoints and Visit Windows

The timepoints and visits for this study are defined in the [Table 1-1](#) “Schedule of Activities”. Any deviation from the study schedule may be reviewed on case-by-case basis at the Blinded Data Review Meeting (BDRM) to determine whether the data should be excluded from the Per-Protocol (PP) analyses.

4 Data Analysis

Data analysis will be performed by [CCI](#) with oversight from GSK CH. The statistical analysis software used will be SAS version 9.4 or higher. For the implementation of graphical approach as described in [Section 4.4](#), SAS IML or gMCP package in R will be used.

Prior to database closure a BDRM will be conducted in which various aspects of the trial will be discussed and agreed.

One aspect that will be considered prior to or during BDRM is the assessment of the number of subjects who have dropped or discontinued from the study due to pandemic related events (e.g., Coronavirus Disease of 2019 [COVID-19]) and the potential need of a sensitivity analysis. Any major changes to planned analyses will need an amendment to SAP.

Except as described below, all listings will be produced for all randomized subjects.

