4.1.2 Protocol Deviations

Protocol deviations will be tracked by the study team throughout the conduct of the study. Data will be reviewed prior to unblinding and closure of the database to ensure all important deviations are captured and categorised. Subjects with important protocol deviations liable to influence the efficacy outcomes will have affected data excluded from the PP analyses. Subjects may also be identified as having important protocol deviations not leading to exclusion of data from the PP analyses.

Important deviations of the protocol procedures may include, but will not necessarily be limited to the following:

- Consent procedures
- Inclusion/Exclusion criteria
- Study procedures
- Non-compliance with product administration
- Inadmissible concomitant medication

The specific details of the important protocol deviations will be listed in Protocol Deviation Management Plan and assessment process will be specified in the Blind Data Review Plan and subjects with important protocol deviations will be identified at the BDRM.

The number and percentage of subjects with at least one important protocol deviation, at least one important protocol deviation not leading to exclusion of data from PP analyses (overall and by each deviation reason) and at least one important protocol deviation leading to exclusion of

data from the PP analyses (overall and by each deviation reason) will be presented by study product (Table 14.1.2) and listed in Listing 16.2.2.1.

All protocol deviations collected on the protocol deviation case report form page will be listed in Listing 16.2.2.2. The listing will present date of deviation, type of deviation, and deviation description.

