4.1.3 Analysis Populations

Four analysis populations are defined.

Population	Definition / Criteria	Analyses Evaluated
Safety	Comprise of all randomized subjects who complete at least one use of study product. Any subject who receives a randomization number will be considered to have been randomized. This population will be based on the treatment the subject actually received.	Safety
Modified Intent-To-Treat (mITT)	Comprise all randomized subjects who complete at least one use of study product and have at least one post-baseline efficacy assessment. Any subject who receives a randomization number will be considered to have been randomized. This population will be based on the study product to which the subject was randomized.	Demographic Baseline Characteristics Efficacy Analysis
Per-Protocol	Comprise all subjects in the mITT population who have at least one assessment of efficacy considered unaffected by protocol violations. Protocol deviations that would exclude subjects from the PP population are defined in Section 4.1.2 (Protocol Deviations). This population will be based on the study product to which the subject was randomized.	Efficacy Analysis
Repeatability Assessment	Comprise of all subjects who have a repeat clinical assessment of efficacy at any visit. There will be a separate population for repeat MLSI assessment and repeat tooth shade assessment: MLSI Repeatability population: Subjects with at least one initial and repeat assessment of MLSI at any visit. VITA Shade Repeatability population: Subjects with at least one initial and repeat assessment of Tooth shade at any visit.	Repeatability analyses

NOTES :

Please refer to [Appendix 1](#): List of Data Displays which details the population to be used for each displays being generated.

The numbers of subjects included in each of the analysis populations will be summarized (Table 14.1.1). Subjects excluded from any of the analysis populations will be listed in Listing 16.2.3.1.

The primary population for assessment of efficacy will be the mITT Population. A PP analysis will be performed on the change from baseline for Mean Total MLSI (A×I) and Mean VITA shade score endpoints only if more than 10% mITT subjects are excluded from the PP Population. A decision on whether a PP analysis will be performed will be made prior to study (unblinding release of the randomization codes).

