4.4.2.1.2 Supportive Analyses

A PP analysis will be performed on the change from baseline in the mean VITA shade score if there is more than 10% difference in the number of subjects between the PP and mITT

populations. A decision on whether a PP analysis will be performed will be made prior to study unblinding (release of the randomization codes).

A summary of the mean VITA shade will be presented for the PP Population in Table 14.2.3.1.2. Statistical analysis of the mean VITA shade score will be presented for the PP population in Table 14.2.3.2.2. In addition, the mean profiles of the mean VITA shade score (Figure 14.2.2.2) at each time point will be plotted by study product for all subjects in the PP Population.

4.4.2.2 Secondary Efficacy Endpoint 2

The Secondary Efficacy Endpoint 2 will be the change from baseline in mean Total MLSI (A×I) score at week 8 and the comparison of each Experimental Dentifrice to the Reference Dentifrice.

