4.4.4 Handling of Missing Values/Censoring/Discontinuations

Missing data will not be replaced or imputed. Subjects who withdraw from the study prematurely will be included in the statistical analyses up to the point of discontinuation.

The use of MMRM analyses account for missing data assuming a missing at random assumption, i.e., there is a systematic relationship between the propensity of missing values and the observed data, but not the missing data.

It is therefore assumed that a subject with missing data would have obtained a similar efficacy result compared to a subject using the same study product with the same smoking status and similar non-missing results at other timepoints (baseline and post-baseline). Sensitivity analyses may be added to the SAP prior to unblinding in case of high drop-out rates and/or exclusion from PP analyses.

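### Does the 10% trigger for the per-protocol analysis need a separate count of excluded Week 8 assessments?

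*Protocol*

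**What the plan says.** Protocol 12.2.1 and SAP 4.1.3 define PP membership in the same way: mITT subjects who "have at least one assessment of efficacy considered unaffected by protocol violations". Neither names a visit.

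Exclusion works on data. Under SAP 4.1.2, subjects with important deviations liable to influence efficacy "will have affected data excluded from the PP analyses". Under SAP 3.4, departures from the visit schedule may be reviewed case by case at the blinded data review meeting "to determine whether the data should be excluded from the Per-Protocol (PP) analyses".

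The trigger works on subjects. Protocol 12.2.2 runs the PP analysis "if there is more than 10% difference in the number of subjects between the PP and mITT populations", and SAP 4.4.1.3 and 4.4.2.1.2 repeat this for the two endpoints. SAP 4.1.3 is stricter in form: the analysis is done "only if more than 10% mITT subjects are excluded from the PP Population". The decision is taken before the randomization codes are released.

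Two other provisions bear on the point. SAP 4.1.2 puts the number of subjects with data excluded from the PP analyses, by reason and study product, in Table 14.1.2, whether or not the trigger fires. SAP 4.4.4 adds: "Sensitivity analyses may be added to the SAP prior to unblinding in case of high drop-out rates and/or exclusion from PP analyses".

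**The concern.** The unit that is excluded and the unit that is counted differ. An assessment is excluded, but a subject is counted, and only when no usable assessment is left. The primary endpoint and the four comparisons in the graphical procedure are all at Week 8. A subject who loses Week 8 and keeps Week 4 stays in PP, so many Week 8 assessments could be set aside while the two populations stay nearly equal in size. In the extreme, if every such subject keeps a usable Week 4 assessment, the difference is 0% at any Week 8 exclusion rate.

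PP membership itself is not at issue. A valid Week 4 assessment contributes to the repeated-measures model, so the subject belongs there. What would be lost is a guarantee: no stated rule would require the Week 8 estimates to be shown without the affected data when such exclusions are frequent.

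**Working it through.** **Inputs from the documents.** 90 evaluable subjects per arm and drop-out of up to 10% before Week 8 (Protocol 12.1). The plan's own figure reproduces: 90 / (1 − 0.10) = 100 per arm, 300 in all, so up to 30 subjects without Week 8. Post-baseline efficacy visits are Week 4 and Week 8. The threshold is more than 10%, so with 300 mITT subjects more than 30 must leave PP.

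**Assumptions.** All 300 are in mITT and attend Week 4. The exclusion rate is the same at both visits, which have the same ±3-day window and the same pre-visit restrictions. An efficacy assessment is read as post-baseline. Let *s* be the subjects affected at both visits by the nature of the deviation, and *n* the further subjects affected at each visit, independently between visits.

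**Step 1: who leaves PP.** A subject leaves only if Week 4 is affected or missing and Week 8 is affected or missing. The loss therefore cannot exceed the number with Week 4 affected or missing.

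**Step 2: everyone attends both visits.** Expected loss = s + n²/(300 − s). The smallest *n* that takes it above 30:

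| s | n | Week 8 excluded | Expected loss |
|---|---|---|---|
| 0 | 95 | 95/300 = 31.7% | 95²/300 = 30.08 |
| 15 | 66 | 81/300 = 27.0% | 15 + 66²/285 = 30.28 |
| 24 | 41 | 65/300 = 21.7% | 24 + 41²/276 = 30.09 |
| 27 | 29 | 56/300 = 18.7% | 27 + 29²/273 = 30.08 |

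If exclusions are fully nested (the same subjects at both visits), the rule fires at 31/300 = 10.3%.

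**Step 3: allow for the planned drop-out.** Thirty subjects have no Week 8 visit. Each of them leaves PP if Week 4 is affected, which has probability (s + n)/270. Expected loss = s + n²/(270 − s) + 30(s + n)/270:

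| s | n | Week 8 excluded | Expected loss |
|---|---|---|---|
| 0 | 77 | 77/270 = 28.5% | 21.96 + 8.56 = 30.51 |
| 15 | 46 | 61/270 = 22.6% | 15 + 8.30 + 6.78 = 30.08 |
| 24 | 19 | 43/270 = 15.9% | 24 + 1.47 + 4.78 = 30.25 |
| 27 | 1 | 28/270 = 10.4% | 27 + 0.004 + 3.11 = 30.12 |

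Fully nested: 28 + 30 × 28/270 = 31.1, so the rule fires at 28/270 = 10.4%. Thirty is the upper planning case. With 15 subjects missing Week 8, the s = 27 and s = 24 rows become 14.7% and 18.6%.

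**Step 4: one example at 20% excluded, s = 15.** With full attendance, 60/300 are excluded and n = 45: 15 + 45²/285 = 22.1, or 7.4% of 300. With drop-out, 54/270 are excluded and n = 39: 15 + 39²/255 + 30 × 54/270 = 15 + 5.96 + 6.00 = 27.0, or 9.0%. The rule is not expected to fire in either case, but in the second it comes close.

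**Reading the results.** The size of the gap depends on how closely exclusions at the two visits coincide. Where deviations persist across visits, the rule behaves almost as if it counted Week 8. It is markedly slow only when Week 8 exclusions are both common and largely unrelated to those at Week 4. Of the categories in SAP 4.1.2, consent and eligibility are fixed at entry and would normally affect both visits. Non-compliance and inadmissible medication may span both. Schedule deviations are judged individually and are not excluded automatically.

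**The case for a change.** The best case for a change is that a numerical trigger fixed before unblinding exists to remove discretion, and here it can miss the visit that matters. SAP 4.4.4 is permissive and has no threshold. Table 14.1.2 gives counts, not a Week 8 estimate without the affected data. The Protocol Deviation Management Plan and Blind Data Review Plan, which are not in the documents, may settle which data are affected, but the trigger would still count subjects. A sentence in three SAP sections and an entry in SAP Section 5 would close the gap, using PP tables already listed in Appendix 1.

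These observations are correct, and the mismatch between data-level exclusion and subject-level counting stands. They do not show that a conclusion of the trial would suffer. The discretion is exercised blind, so it cannot be steered by the results. The wording of SAP 4.4.4 refers to exclusion from PP analyses, which fits data-level exclusion, so the team has a stated route to the Week 8 analysis if the review shows many exclusions. A second 10% cut on a Week 8 denominator would be no better justified than the present one. Choosing a fixed number over blinded judgement for a supportive analysis is a preference.

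**Conclusion.** The point is accurate as a reading of the text, but it does not call for a change. A Week 8-only exclusion with a usable Week 4 assessment does not count towards the 10%. With 300 mITT subjects, 30 lacking Week 8 and equal exclusion rates at the two visits, the trigger is first expected to fire at between 10.4% and 28.5% of Week 8 assessments excluded. It fires at about 10% when exclusions fall on the same subjects at both visits. These are expected values under assumed patterns; the documents give no exclusion rates, and nothing in them points to frequent Week 8-only exclusions.

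The consequence is confined to whether a supportive analysis is mandatory. Efficacy is judged on mITT, and the success criterion in Protocol Section 3 and the graphical procedure do not refer to PP. Exclusions are reported by reason and product in all cases. At the blinded data review the team can look at how many Week 8 assessments are excluded for each endpoint and, if there are many, use SAP 4.4.4. That is a sensible way to fill the gap and needs no amendment.
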